AIM 3 Rationale and Design: rTMS can improve cognition in PD without dementia⁵², PD with depression⁸⁰, older adults¹²² and in AD¹²³ but has not been tested in PD-MCI. Given the need for improved cognitive treatments and possible differences in rTMS effects on PD-MCI pathophysiology it is important to specifically test rTMS in this population. Prior studies as well as our own pilot data suggest that rTMS modulates cortical connectivity,^{16,17} thus rTMS provides not only a potentially effective intervention but an important causal test of our associative data and theoretical link between cortical connectivity and cognitive dysfunction in PD. Our *clinical objective* for this experiment is to determine whether rTMS improves cognitive outcomes in PD-MCI. Our *mechanistic objective* is to determine whether rTMS normalizes patterns of cortical connectivity. We *hypothesize* that high-frequency bifrontal rTMS will partially normalize patterns of cortical connectivity linked to frontal nodes and will improve cognitive measures. To test this hypothesis 55 PD-MCI subjects will be randomized to a 10-day course of real or sham bifrontal high frequency rTMS. We will measure cognitive and MEG outcomes pre-treatment and on the day of the last treatment (neuropsych testing and MEG procedures may be separated by 1 day if patient is fatigued) and repeat cognitive measures 28 days post rTMS to assess the durability of cognitive changes.

TMS: TMS will be administered using a 70-mm diameter air-cooled figure-of-8 coil and SuperRapid² Magstim Stimulator. We will first define the subject's resting motor threshold (MT) by localizing the hand area of motor cortex and determining the minimal TMS amplitude needed to produce a motor-evoked potential of 50 microV on 4 of 8 trials measured by EMG over the first dorsal interosseous muscle (Biopac, Goleta, CA). Once the MT is determined, repetitive pulses will be delivered to the right and left pre-frontal cortex (Brodmann area 46) using a frameless stereotactic navigation system and the subject's MRI in Brainsight software. Depending on our preliminary results from Aim 1, we may change our target if it is evident that a particular frontal node shows high clustering within beta or theta frequency bands. This type of targeting based on functional data has been previously performed and may enhance TMS effects on intrinsic connectivity.¹⁶ Stimuli will be delivered at 20 Hz at 90% rMT for 25 trains of 30 pulses per train, inter-train

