interval of 30 seconds for a total of 750 pulses per hemisphere, which is well within the most recent international TMS safety guidelines.¹²⁹ This dose and duration of rTMS is based on physiological studies of healthy adults and treatment studies of cognition in PD and Alzheimer’s disease.^{52, 123} Side of first stimulation (left vs right hemisphere) will be counterbalanced across subjects. Sham stimulation will be delivered using a sham coil fitted with electrodes to mimic both the auditory and somatic sensation of real TMS as I have performed in prior TMS trials.¹⁹

Schedule of Procedures

	Baseline Procedures ²	← 2 weeks →			28 days post-rTMS Session 10 ¹
		rTMS Session 1 ¹	rTMS Sessions 2-9 ¹	rTMS Session 10 ¹	
Informed consent	X				
MRI (anatomical and optional functional scans)	X				
MEG	X			X ¹	
Neuropsych tests	X			X ¹	X ¹
rTMS (real or sham) ¹		X ¹	X ¹	X ¹	
Randomization to real or sham TMS ¹	X				

¹PD-MCI subjects only

²Baseline procedures to be completed within 1 week of rTMS Session 1

D. Description, Risks and Justification of Procedures and Data Collection Tools:

PD-MCI and mild dementia patients may be considered a vulnerable population due to cognitive dysfunction but are necessary to answering our research questions. We are cognizant of this issue and will carefully assess potential participant’s understanding of the study, particularly of study activities and risks. If there are any concerns on the part of the investigator or potential participant, we will require that their guardian participate in the consenting process and sign an informed consent. We will also require that PD-MCI subjects give consent, or at minimum assent if fully informed consent is not possible. Our protocol and consent forms will be approved by our local IRB before approaching any potential subjects.

After enrollment and screening assessment, PD and PD-MCI subjects will undergo neuropsychological testing, magnetoencephalography (MEG) recordings, and MRI. PD-MCI subjects will then be randomized in a 1:1 ratio to real or sham TMS groups using MAPLE 9.0 software (Waterloo, Canada). Baseline neuropsychological testing, MEG, and MRI may be performed over multiple days, but all will be completed within 1 week and within 1 week of first TMS session for PD-MCI subjects.

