AIM 2 Statistical Analysis and Sample Size: We will use SVM to determine what combination of MEG features yields the most robust classifier for discriminating PD with and without MCI. The principle behind SVM learning is that features of interest can be modeled in a high-dimensional feature space (see Figure 2 for a visualization of a very simple 2 feature space). SVM then uses a recursive algorithm to define a hyper-plane of select features creating the greatest distance between groups of interest.¹¹⁹ Given the large potential combination of MEG features and sensors this will be a computationally intensive but tractable SVM application. As the optimal number of features to build an SVM classifier is not known a priori, we will use a procedure called bagging-cross-validation to determine the optimal number of features and maximize the information gained from SVM in this relatively small sample size.¹²¹ This approach uses a boot-strap leave one out procedure to create $n - 1$ training sets and n test subjects, where n is the total sample size, to optimize feature number and maximize the final receiver operating curve. Given the large effect sizes seen in our pilot data and other MEG studies of PDD⁵⁸, we anticipate that our *sample size* of 45 (allowing for 5 unusable data-sets from the original 50) will allow us to create a classifier with an area under the ROC curve (AUC) of 0.95 or higher comparable to AUCs seen in other SVM applications in dementia and MCI populations with as few as 15 subjects per group.⁶⁸

AIM 3 Statistical Analysis and Sample Size: We will address our primary clinical research question by determining whether there is a significant group difference between the real and sham treated PD-MCI patients on the MDRS change following rTMS using repeated measures ANOVA. We will address our primary physiologic research question by determining whether there is a significant difference between the real and sham treated PD-MCI patients on change in MEG measures of small-worldness using a repeated measures ANOVA. Planned secondary analyses will include determining group differences in change on measures of quality of life, domain specific neuropsychological results and durability at the 28-day post-TMS time point. If cognition is improved we will use regression modeling to determine if these improvements were associated in changes

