in small-worldness or other MEG features. With a total *sample size* of 50 (25 per group allowing for 5 drop-outs from original 55) we will be able to determine a between group difference of 10 points on the MDRS (assuming a SD of 13 as per prior trials and an effect size 0.77)¹²⁴ with 80% power and 0.05 significance. This sample size is comparable to prior PDD studies. For example, a study of rivastigmine in PDD detected significant change on the Mattis with only 28 subjects.¹²⁴

Exploratory Aim Statistical Analyses and Sample Size: We will address our exploratory research questions by looking at Spearman correlations or linear models of MEG and MRI measures. Power considerations are similar as for Aim 1 with detection of correlations of 0.18 or higher between our MEG and MRI features with 80% power 0.05 significance.

G. Summarize Knowledge to be Gained:

PD is the second most common neurodegenerative disease, affecting over one million Americans and dementia is the most common cause of nursing home placement in this population.^{53, 54} Our understanding of the neurobiological mechanisms of cognitive dysfunction in PD are limited and we do not have efficacious treatments. This research will address this significant public health issue in three major ways: 1) Identify abnormalities in cortical connectivity associated with cognitive dysfunction in PD; 2) Develop a MEG biomarker for cognitive dysfunction in PD; and 3) Evaluate the potential for TMS to induce durable changes in PD cognitive function and connectivity. Given the burden of dementia in this population, we feel that the minimal risks involved are justified both to individual PD and PD-MCI subjects, the larger population of PD and PD-MCI patients, and to society as a whole. Recent TMS studies using published safety guidelines suggest that the risks of TMS may be even lower than previously described. Even using conservative estimates and anticipating some discomfort from prolonged sitting and cognitive testing, we argue that this research is imperative to advance this field and ultimately to provide relief to these patients and their caregivers.

H. References:

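### The primary Aim 3 test of MDRS change is a repeated measures ANOVA with no named visits, no analysis-as-randomised rule and no missing-data method, although five drop-outs are expected

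*Combined protocol and SAP*

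**What the plan says.** The Aim 3 design (section IV.C) states that "55 PD-MCI subjects will be randomized to a 10-day course of real or sham bifrontal high frequency rTMS", and section IV.D gives allocation as "randomized in a 1:1 ratio to real or sham TMS groups". On timing, section IV.C says: "We will measure cognitive and MEG outcomes pre-treatment and on the day of the last treatment". Cognitive testing is repeated 28 days after the last session. The Schedule of Procedures agrees: neuropsychological tests at baseline, session 10 and day 28; MEG at baseline and session 10 only.

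In section IV.F, under the Aim 3 statistical analysis, the primary clinical test is for a "group difference between the real and sham treated PD-MCI patients on the MDRS change following rTMS using repeated measures ANOVA". The primary MEG outcome, change in small-worldness, is also tested by repeated measures ANOVA. Durability at day 28 is listed among the planned secondary analyses.

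The sample size is 50, explained as "25 per group allowing for 5 drop-outs from original 55". It targets a "between group difference of 10 points on the MDRS", "assuming a SD of 13 as per prior trials and an effect size 0.77", "with 80% power and 0.05 significance".

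Section IV.E recognises that retention may be hard over two weeks of daily sessions. Its answer concerns conduct: it will use procedures like those of an earlier rTMS trial that kept all its patients. No section defines an analysis population, a missing-data method or a sensitivity analysis for losses.

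**The concern.** Randomisation protects the comparison of the 55 patients allocated, not of whichever subset has complete data. Classical repeated measures ANOVA needs a value at every modelled visit and omits patients who lack one. The protocol expects about five losses and says nothing that would override that default.

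Two things are at stake. First, information already collected is thrown away: if the model holds baseline and session 10, a patient who misses the session-10 test but attends at day 28 contributes nothing. Second, if patients who leave before session 10 tend to be doing worse (or better), and more leave one arm than the other, the difference among completers is shifted even when treatment has no effect. With about 25 patients per arm, a few such losses are enough to move the estimate. Because the visits in the model are not named, the set of patients analysed could also be settled after the data are seen.

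**Working it through.** **1. The plan's own figures.** The loss allowance is consistent: 55 − 5 = 50, and 5/55 = 9.1%. The standardised effect is 10/13 = 0.77, as stated. The noncentrality at 25 per arm is 10 / (13 × √(2/25)) = 2.72. Two-sided power at 0.05 is then Φ(2.72 − 1.96) = 77.6% by the normal approximation and 76.0% by the t distribution, somewhat below the stated 80%. If all 55 (28 vs 27) had a session-10 value, the t-test power would be 79.95%. The plan does not state sidedness or whether the SD of 13 is of the score or of the change. I take the test as two-sided and the SD as that of change.

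**2. Who is omitted under each reading of the ANOVA.**

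| Patient's MDRS record | Model: baseline, session 10 | Model: baseline, session 10, day 28 |
|---|---|---|
| Baseline only | omitted | omitted |
| Baseline and day 28, no session 10 | omitted | omitted |
| Baseline and session 10, no day 28 | kept | omitted |

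Three features favour the two-visit reading: day-28 durability is a secondary analysis, the design text separates it from the before-and-after measures, and the parallel MEG test cannot have a day-28 visit because no scan is scheduled then.

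**3. Bias by arithmetic.** If k of n patients in an arm are lost and their mean change is g points worse than that of completers, the arm mean is overstated by (k/n) × g. For five losses from an arm of 28:
- g = 6.5: 5/28 × 6.5 = 1.2 points
- g = 13: 5/28 × 13 = 2.3 points
- g = 19.5: 5/28 × 19.5 = 3.5 points

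Losses in both arms largely cancel. With g = 13 in each arm, a 3/2 split gives 3/28 × 13 − 2/27 × 13 = 1.39 − 0.96 = +0.4 points. A 2/2 split gives 0.93 − 0.96, about 0.

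**4. Simulation of loss before session 10.** Assumptions: no true effect, SD of change 13, 28 real and 27 sham, two-sided 0.05 t test on completers. Except for random loss, the patients lost are those with the lowest values of a score that has the stated correlation with change.

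| Losses real/sham | Correlation with change | Bias (MDRS points) | Rejection |
|---|---|---|---|
| 5/0 | 0 (random) | about 0 | about 5% |
| 2/2 | 0.5 | about 0 | 5.4% |
| 3/2 | 0.5 | +0.4 | 5.7% |
| 5/0 | 0.5 | +2.0 | about 9% |
| 3/2 | 1.0 (poorest responders) | +0.7 | 8.0% |
| 5/0 | 1.0 (poorest responders) | +4.0 | about 22.5% |

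The direction follows the arm that loses more: four losses from sham only, at correlation 0.5, give −1.7 points. The last row is a bound, not a forecast.

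**5. Simulation of loss after session 10.** Five real-arm patients miss day 28, with the chance of loss weighted towards poor change (weight exp(−change/13)) and an assumed within-patient correlation of 0.5. A baseline/session-10 ANOVA keeps all 55: bias −0.1, rejection 5.0%. A three-visit ANOVA on completers shifts the session-10 difference by +2.1 points and rejects the group-by-time test in 7.3% of runs.

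**The case against.** A reader might infer that withdrawal after the session-10 visit biases the primary MDRS result. The documents do not support that. It requires day 28 to be in the primary ANOVA, and the three features listed with the table of omitted patients point the other way. On the two-visit reading a missed day 28 removes nobody. What remains is that the protocol never says which model it means.

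A reader might also take the allowance for five drop-outs as a rule excluding them from analysis. It is ordinary sample-size inflation and states no such rule. Likewise, complete-case deletion is a property of the standard method, not something the protocol declares. Both points stand. Even so, with no other rule given, deletion is what the named method does by default.

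The size of the problem can be overstated. Patients who see no benefit might leave sham as readily as real treatment, and roughly balanced losses at moderate correlation give almost no bias. Planned loss is only about 9%, the protocol cites full retention in an earlier trial, and it calls its own sample relatively small, with a larger trial to follow. These points limit the expected harm. They do not supply an analysis rule.

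Finally, a mixed model gains little for a patient who leaves during the treatment weeks with only a baseline score. That is correct, and it is why the model alone is not enough.

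**Conclusion.** The concern holds in this form: the primary Aim 3 analysis uses a method that by default drops patients with a missing modelled visit, and the plan does not name the visits, state analysis as randomised or test the effect of losses. A session-10 absentee who returns at day 28 would be discarded. Loss before session 10 can bias the comparison only if it is both outcome-related and unequal between arms.

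At a correlation of 0.5 between loss and change, the bias runs from about 0 (2/2) through +0.4 points (3/2) to about +2 points (5/0), against a 10-point target, with false rejection from 5.4% to about 9%. These figures rest on assumed loss patterns and on reading the SD of 13 as the SD of change; the documents give no expected split by arm or reason for loss. Loss after session 10 matters only if day 28 is placed in the same ANOVA, which the text does not say and its structure argues against. This should be corrected because the better method is available at almost no cost, not because a large bias is likely.

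**What to change.** In section IV.F, replace the repeated measures ANOVA for MDRS with a linear mixed model for repeated measures:
- include all randomised patients in their assigned arm;
- use every available MDRS value at baseline, session 10 and day 28, with unstructured covariance;
- make the arm difference in change at session 10 the primary contrast, and take the day-28 difference from the same model as the secondary contrast.

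Add one delta-type sensitivity analysis: shift the assumed session-10 values of drop-outs by increasing amounts, including shifts that differ between arms, until the conclusion changes. This covers patients with only a baseline score, for whom the mixed model recovers little. State that MEG change is also analysed as randomised.

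The cost is a paragraph of plan text and a little more analysis work, with no extra patients or visits. With complete data the mixed model essentially reproduces the ANOVA. The downside is reliance on missing at random, which the sensitivity analysis is there to probe.

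### Aim 3's primary MEG test needs two usable recordings per patient, but the only Aim 3 sample figure deducts drop-outs alone and the stated repeated measures ANOVA would discard patients with one bad scan

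*Combined protocol and SAP*

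**What the plan says.** Section IV.C (Aim 3 Rationale and Design) states that "55 PD-MCI subjects will be randomized to a 10-day course of real or sham" rTMS. Section IV.D sets the allocation: "PD-MCI subjects will then be randomized in a 1:1 ratio to real or sham TMS groups". Section IV.C and the Schedule of Procedures place MEG at two times, baseline and rTMS Session 10.

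Section IV.F (Aim 3 Statistical Analysis and Sample Size) names two primary questions. The clinical one is MDRS change. For the other it says: "We will address our primary physiologic research question by determining whether there is a significant difference between the real and sham treated PD-MCI patients"; the outcome compared there is how far small-worldness changes. Both use repeated measures ANOVA. One sample statement follows: a total of 50, "25 per group allowing for 5 drop-outs from original 55", to detect "a between group difference of 10 points on the MDRS". Its inputs are given as "assuming a SD of 13 as per prior trials and an effect size 0.77", and its error rates as "with 80% power and 0.05 significance". No number of patients, detectable effect or missing-scan rule is given for the MEG question.

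The other aims in section IV.F do allow for unusable MEG data, and they need only one recording. Aim 2 plans on 45, "allowing for 5 unusable data-sets from the original 50". Aim 1, which uses the same recordings, makes the same step from 50 to 45 but lets the 5 be drop-outs, unusable data, or both. Section IV.B lists drop-outs and unusable datasets among the reasons for asking to recruit up to 150.

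**The concern.** The plan budgets for unusable scans where one scan is needed and makes no such allowance where two are needed. The usual repeated measures ANOVA needs both values from each patient, so a bad recording at either visit loses the good one as well. A patient can complete treatment and cognitive testing, count among the 50 for the MDRS, and still be absent from the primary physiologic test.

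That test is Aim 3's mechanistic objective, and section IV.C presents it as a causal check on the associations sought in Aim 1. If 50 is the only sample figure in view, a null MEG result may be read as stronger evidence than it is, and usable recordings will have been thrown away.

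**Working it through.** **1. The plan's own figure.** 55 − 5 = 50, and 50 / 2 = 25 per group. This reproduces exactly. The stated effect size also follows: 10 / 13 = 0.769, printed as 0.77.

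**2. The unusable-scan rate.** Aim 2: 5 / 50 = 10%, all attributed to unusable data. Aim 1: the same 5 of 50, with drop-outs included. So 10% is an upper allowance, and the rate for unusable data alone is not given. I use u = 10%, and u = 5% as an assumed lower value.

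**3. Complete MEG pairs among the 50 completers.** If the same patients fail at both visits, pairs = 50(1 − u). If the two recordings fail independently, pairs = 50(1 − u)². Both are assumptions; the plan says nothing on this.

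**4. Detectable effect.** Two-group comparison of mean change, one two-sided test at 0.05 (sidedness assumed, since the plan does not state it), 80% power, noncentral t with n per arm, 2n − 2 degrees of freedom and noncentrality d√(n/2). Effects are in SDs of the change.

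| Assumption | Complete pairs | Per arm | Detectable effect |
|---|---|---|---|
| No unusable scans | 50 | 25 | 0.81 |
| u = 5%, same patients | 50 × 0.95 = 47.5 | 23.75 | 0.83 |
| u = 5%, independent | 50 × 0.95² = 45.1 | 22.6 | 0.85 |
| u = 10%, same patients | 50 × 0.90 = 45 | 22.5 | 0.85 |
| u = 10%, independent | 50 × 0.90² = 40.5 | 20.25 | 0.90 (0.91 at 20) |

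The reference value at 25 per arm is 0.81 rather than the plan's 0.77 because, by this calculation, 25 per arm gives about 76% power at 10/13, not 80%. That is a separate MDRS matter and is not counted here.

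**5. What a mixed model recovers.** Take u = 10% with independent failures. Per arm there are 25 × 0.81 = 20.25 complete pairs, 25 × 0.9 × 0.1 = 2.25 with baseline only, 2.25 with the last session only, and 0.25 with neither. With equal variances and correlation ρ between visits, the information on mean change rises by the fraction m(1 − ρ)/n, where m = 2.25 and n = 20.25.

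- ρ = 0.3 (assumed): 2.25 × 0.7 / 20.25 = 7.8%
- ρ = 0.8 (assumed): 2.25 × 0.2 / 20.25 = 2.2%

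The gain is therefore about 2 to 8%. It is larger if the two arms are given a common baseline mean, which randomisation justifies. If the same patients fail both times, there are no single scans to recover.

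**The case against.** The strongest reply is that nothing in the plan is miscalculated. The 25 per group belongs to a sentence about the MDRS, which needs no MEG, and no sentence attaches it to small-worldness. This stands: a reader might infer that the 25 per group is an arithmetic error, and the documents do not support that. What is left is a primary question with no sample statement of its own.

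A reader might also infer that the plan's own allowance leaves 20 to 22 patients per arm. It does not. Aim 1 folds drop-outs into the same 5, so deducting drop-outs and then a full 10% may count some losses twice, and the lower end needs two independent failures, which is an assumption. Hence the wider range above.

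A third tempting step is to quote a loss of MEG power at an effect of 0.77. That value is 10/13 on the MDRS, and no effect size is given for change in small-worldness.

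There are mitigating features. The ceiling of 150 compares with 80 planned (25 + 55). Baseline MEG comes before randomisation, so a failed scan might be noticed in time. Only 30 seconds of clean data (five epochs of 6 seconds) are needed from each two-minute condition, and artifact correction is available. These could lower the loss. But no rule for repeating a scan or replacing a patient is written, drop-outs are covered by the same ceiling yet are still deducted from 55, and none of this provides for a recording that fails at Session 10.

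Finally, section IV.E already concedes that the sample is fairly small. That is a general caution and does not address incomplete MEG pairs.

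**Conclusion.** The point holds as a gap in the MEG part of Aim 3, not as an error in the MDRS sample size. With any unusable scan among the completers, the stated ANOVA has fewer than 50 complete pairs: about 45 to 47.5 at an assumed 5% unusable rate per scan, and about 40 to 45 at 10%. The detectable effect moves from 0.81 to between about 0.83 and 0.91 SD of the change.

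This rests on the assumed rate, on how far failures at the two visits coincide, and on a single two-sided test at 0.05. Section IV.A analyses six frequency bands separately, and Aim 3 names neither a band nor a correction. As an illustration, a Bonferroni correction over six would put the detectable effect at about 1.08 to 1.15 SD for 22.5 to 20 pairs per arm. The shift due to unusable scans is modest, but it is avoidable in part and cheap to disclose.

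**What to change.** 1. Analyse small-worldness with a likelihood-based mixed model with time, group and group-by-time, preferably with a common baseline mean for the two arms. Patients with one usable recording then contribute.
2. State in the Aim 3 sample size paragraph that 50 applies to the MDRS. Give separately the expected number of complete MEG pairs and the detectable effect, labelled as assumption-based and as before any correction for the six frequency bands.

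The cost is a slightly more model-dependent analysis, since the single-scan patients are used under a missing-at-random assumption, and a less favourable printed figure for the MEG question. The gain in precision from the single scans is small (about 2 to 8% in the case worked above). No patients or visits are added.

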All subjects will be required to wear hearing protection and will be supervised by study personnel during all aspects of this study. A neurologist will be available either in person or on-call within the building in the event of a seizure or other adverse study event. Study personnel involved in human subject interactions will be trained not only in human subjects protection but will be also BLS or ACLS certified and specifically trained in seizure safety and what to do in the event of other medical emergencies. There is a COR cart available outside of the TMS and MEG laboratories. All adverse events will be reported to the IRB within 5 days and seizures or other significant adverse events associated with TMS will additionally be reported to the FDA.

E. Potential Scientific Problems:

Prior TMS trials are often questioned regarding the adequacy of patient blinding with certain sham procedures. Our sham involves both auditory and tactile stimulation, and in fact resulted in a similar improvement in depression as real TMS in our recent trial.¹⁹ Subject retention, particularly with PD-MCI, may be difficult with 2 weeks of daily treatment. We will use similar procedures to our PD apathy rTMS trial where we maintained 100% retention. Finally, our sample size is relatively small to detect clinically significant changes. This is in part due to budgetary limitations and one goal of this trial is to serve to develop a more definitive, larger trial with longer-term follow-up. Changes in sensor location over repeated recordings may result in false attribution of brain activity

changes. To address this issue, sensors will be realigned to a common sensor array to allow repeated group level analysis in a shared brain space.¹⁰⁹

F. Data Analysis Plan:

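### Aim 3 power does not follow from its inputs: effect size 0.77 with 25 per group gives about 76%, not 80%, and the plan does not say what the SD of 13 measures

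*Combined protocol and SAP*

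**What the plan says.** The randomised comparison is described in section IV.C, Aim 3 Rationale and Design: "55 PD-MCI subjects will be randomized to a 10-day course of real or sham bifrontal high frequency rTMS". Section IV.D sets the allocation at 1:1. Section IV.F, Aim 3 Statistical Analysis and Sample Size, defines the primary clinical question as the difference between real and sham "on the MDRS change following rTMS using repeated measures ANOVA".

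The same section gives an analysed total of 50, described as "25 per group allowing for 5 drop-outs from original 55". It states that this number can detect a "between group difference of 10 points on the MDRS (assuming a SD of 13 as per prior trials and an effect size 0.77"), with 80% power at the 0.05 level. It does not give the sidedness of the test, the type of SD, or a correlation between the pre- and post-treatment scores.

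Section IV.E acknowledges that "our sample size is relatively small to detect clinically significant changes" and says that one purpose of the trial is to prepare a larger one.

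**The concern.** The paragraph supplies everything needed to check its own power figure, and the figure comes out too high for a two-sided test and too low for a one-sided test. This is the power statement for the primary clinical question of the randomised part of the study. A null result would be read against a claimed 20% risk of missing a 10-point effect. If 13 is the SD of change, that risk is about 24%.

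The undefined SD matters more. The analysis is of change, and the SD of change can be well above or well below the SD of a single score, depending on the pre-post correlation. If 13 is a single-score SD, the power of the planned analysis cannot be read from the plan at all. Because the trial is meant to inform a larger one, a mislabelled SD or an inflated power figure could carry over into that design.

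**Working it through.** **Inputs** (section IV.F, Aim 3, except allocation, which is in IV.D)

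- Difference: 10 points
- SD: 13, type not stated
- Effect size: 0.77
- Analysed: 25 per arm, 1:1
- Significance: 0.05, sidedness not stated
- Claimed power: 80%

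**Step 1. Effect size.** 10/13 = 0.769, so 0.77 is consistent with the stated difference and SD.

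**Step 2. The test.** With two groups and two time points (pre-treatment and the last treatment day), the group-by-time F test of the repeated measures ANOVA is the square of the two-sample t test on change. One power calculation therefore serves for both.

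**Step 3. Attempt to reproduce 80%.** The noncentrality is d × √(n/2) = 0.77 × √12.5 = 2.722.

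| Version, 25 per arm, d = 0.77 | Power |
|---|---|
| Two-sided t, 48 df | 76.0% |
| F(1, 48), noncentrality 2.722² = 7.41 | 76.0% |
| Two-sided normal approximation: Φ(2.722 − 1.960) = Φ(0.762) | 77.7% |
| One-sided t | 85.1% |
| One-sided normal approximation: Φ(2.722 − 1.645) = Φ(1.077) | 85.9% |

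A simulation of 100,000 runs also gave 76.0% for the two-sided test. With d = 10/13 unrounded, the two-sided figures are 75.96% (t) and 77.6% (normal). None of these is 80%.

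**Step 4. What would give 80% (two-sided, d = 0.77).**

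- By t test: 27 and 27 gives 79.3%; 27 and 28 gives 80.0%. That is 55 analysed.
- By normal approximation: 26 and 26 gives 79.3%; 26 and 27 gives 80.0%; 27 and 27 gives 80.8%. That is 53 to 54 analysed.
- Keeping 25 per arm, by t test: d must be 0.809, and 0.809 × 13 = 10.5 points.
- Keeping 25 per arm, by normal approximation: d must be 0.792, and 0.792 × 13 = 10.3 points.
- Keeping 25 per arm and 10 points, by t test: the SD of the analysed outcome must be no more than 10/0.8087 = 12.37.

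The claimed 80% matches the 55 randomised. Whether it was in fact calculated on 55 cannot be known from the documents.

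**Step 5. If 13 is the SD of a single score.** With equal SDs before and after treatment, SD of change = 13 × √(2(1 − r)). The values of r are assumptions; the documents give none.

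| Assumed r | SD of change | d = 10/SD | Power, two-sided t, 25 per arm |
|---|---|---|---|
| 0.3 | 15.38 | 0.650 | 61.5% |
| 0.5 | 13.00 | 0.769 | 76.0% |
| 0.7 | 10.07 | 0.993 | 93.1% |

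Power reaches 80% at r = 0.548. Check: 12.37²/(2 × 13²) = 153.0/338 = 0.453, and 1 − 0.453 is about 0.55.

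**The case against.** The arithmetic is not in dispute. The case against is about how much it shows.

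- **The 76% is conditional.** The plan never says that 0.77 is the standardised effect for change; it is simply 10/13. If 13 is a single-score SD, a correlation of about 0.55 gives 80%. This stands as a condition on the 76% figure. It does not support the 80%, because the plan states no such correlation.
- **A three-visit analysis comes close.** Cognitive testing is also scheduled 28 days after treatment. Assume SD 13 at each visit, a common correlation of 0.5, and a 10-point benefit held to day 28. The noncentrality is then 12.5 × 66.67/84.5 = 9.86, and the group-by-time F(2, 96) test has 79.7% power. This again needs assumptions that the plan does not make, and section IV.F makes durability at 28 days a secondary question.
- **The gap is small.** It is four points of power by t test and 2.3 by normal approximation. An SD of 12.4 instead of 13 would close it, which is within ordinary planning uncertainty. This is a fair limit on the weight of the point, but the figure still does not follow from the inputs given.
- **The plan admits the sample is small.** Section IV.E does so and cites the budget, but it does not correct or qualify the 80%.
- **The cited source may define the SD.** The sample-size paragraph cites reference 124, while the numbered list in the protocol ends at 42. Whatever the source says, the protocol should state which SD it uses.

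**Conclusion.** The concern holds. Taking 0.77 as the standardised effect for the planned comparison, with 25 analysed per arm and a two-sided 0.05 test, power is 76% by t test or 78% by normal approximation, against 80% stated. One-sided testing does not explain the figure either. The allowance for five drop-outs does not preserve the stated power, because 80% by t test needs all 55.

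The proven shortfall is modest. It is four points of power, or half a point on the MDRS in the detectable difference, and it rests on 13 being the SD of the outcome analysed. If 13 is a single-score SD, the true power could be clearly below or clearly above 80%, and the plan does not allow a reader to tell which. Nothing here shows that the design or the analysis is unsound. The power statement should be corrected.

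**What to change.** 1. State whether 13 is the SD of the MDRS change or of a single score, and state that the test is two-sided if that is intended.
2. If it is the SD of change, restate the power: with 25 evaluable per arm and two-sided 0.05, 76% for a 10-point difference, or 80% for about 10.5 points (d = 0.81).
3. If it is a single-score SD, state the assumed pre-post correlation and its basis, and recompute the power for the change comparison.

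The cost is one or two sentences. No extra patients are needed, and the design and analysis do not change. If 13 is the SD of change, the stated power becomes slightly less favourable.
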